5.2.2 Unblinding Procedure

Blinding of participants and therapists to condition is not possible as it will be clear to both therapists and patients which treatment is given.

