treatment (1.0), the number of persons needed to include is 50 persons per condition to reach for 80% power. Expecting a dropout rate of 25%, we will include 63 persons per arm, for 4 arms a total of 252 adult patients with PTSD and - at least 4 - PD symptoms. Of these patients, 80 next to 40 healthy matched controls will be asked for additional MRI research before and after treatment. In total, 292 persons will be included in this study.

Intervention: In patients with PTSD and BPD: EMDR (3-6 months plus 6-9 months treatment pause) compared to integrated DBT-EMDR (12 months); in patients with PTSD and CPD: ImRs (3-6 months plus 6-9 months treatment pause) compared to integrated ImRs-SFT (12 months).

Main study parameters/endpoints: Primary outcome measure is PTSD symptom severity after 12 months. Secondary outcome measures are PD symptoms (SCID-5-PD), disability (WHODAS), quality of life (EQ-5D-5L) and health costs (Tic-P). At baseline (T₀) and after 12 months (T₄) clinical interviews (CAPS-5, SCID-5-PD dimensional score) and self-rating scales (PCL-5) will be used. After 3 (T₁), 6 (T₂), 9 (T₃), and 18 months (follow-up), questionnaires only will be used. At baseline, candidate predictors will be measured including above mentioned cognitive, affective, relational factors, and hormonal and epigenetic factors. In a subgroup, structural and functional MRI, with resting-state and an emotion processing (face recognition) will be performed.

Nature and extent of the burden and risks associated with participation and benefits:

The burden and risks associated with participation in this study is reasonable. All patients will receive psychotherapy, which is considered to be the most effective treatment for PTSD and PD. There is evidence that all four conditions are therapeutic in patients with PTSD and PD and no evidence yet what condition is more effective. Total time of the six measurements is approximately 5 hours per patient for interviews and 5 hours for questionnaires (see table 3), which are partly part of the routine outcome measurements (ROM). Questionnaires can be filled in at home. On the one hand, extensive clinical interviews and self-rating scales can be felt as disturbing because of fatigue, taken time and emotional burden. On the other hand, patients may feel well recognized by the time taken by specialized clinicians for them. Assessors will be well-trained and work in close

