connection with the treatment teams. For predicting treatment response, biological and genetic measures are integrated in the study. These measurements include physical examination, blood samples and hair samples. The burden and risk associated with the baseline blood sample and hair sample is reasonable. For the subgroup of MRI research, participants will twice have a 60-minute MRI session during which they will perform affective-laden tasks during scanning. Functional MRI is a commonly used technique that is considered to be safe if you follow the safety instructions (e.g. no metal objects in the MRI room) and contraindications (e.g. no metal implants, not pregnant, no seriously claustrophobia). Lying in the scanner while performing affective-laden tasks in the scanner can occasionally give patients uncomfortable feelings of anxiety and distress by reliving of their traumatic experiences. During and after the scan procedure a debriefing will be held to cover this by the executor of the scan protocol. The principal investigators of this study have long experience with symptom provocation in the scanner ([name]: early traumatized PTSD patients with comorbid personality disorders: only 1 in 33 patients had a panic attack; [name] in patients with panic disorder, PTSD, OCD, Tourette, Parkinson, hypochondriasis: panic attacks were rare and not more frequently than healthy controls). In all, we consider the risk and burden associated with participation to be low.

There are no benefits for individual patients participating in this study. Benefits for PTSD patients as a whole are that this study will provide important information about profiling patients guiding optimal treatment choices base on individual prediction models in patients with both PTSD and personality problems. It will help to know what works for whom and personalize mental health care as short as possible and at the main time most effective. It will help to understand why

(working mechanisms) what treatment works best for whom.

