5. METHODS

5.1 Study parameters/endpoints

5.1.1 Primary outcome parameters

○ Severity of PTSD (DSM-5) as measured with:

- CAPS-5 (Clinician Administered PTSD Scale, Weathers et al., 2014, Boeschoten et al., 2014). The first psychometric evaluation of the CAPS-5 showed good reliability, convergent and divergent validity (Weathers et al., 2017). Severity of PTSD is measured on a continuous scale on the CAPS-5. All 20 symptoms of PTSD from the DSM-5 are assigned a severity score of 0-4. These 20 scores are then summed to calculate total PTSD symptom severity.

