5.2 Randomisation, blinding and treatment allocation

5.2.1 Randomization

An independent central research assistant will randomize participants to condition after checking all in- and exclusion criteria. Randomization will be based on block randomization (n=4 per block) per site, to guarantee a balance between conditions per site and over time. For both RCTs there will be a separate randomization procedure depending on comorbid PD diagnosis:

- A1. If PTSD + BPD: EMDR vs. integrated DBT-EMDR
- A2. If PTSD + CPD: ImRs vs. integrated SFT-ImRs.

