6.2.2. Serious adverse events (SAEs)

We do not expect any serious adverse event (i.e. any untoward medical occurrence or effect that results in death; is life threatening (at the time of the event); requires hospitalisation or prolongation of existing hospitalisation; results in persistent or significant disability or incapacity; is a congenital anomaly or birth defect; any other important medical event that may not result in death, be life threatening, or require hospitalization, may be considered a serious adverse experience when, based upon appropriate medical judgement, the event may jeopardize the subject or may require an intervention to prevent one of the outcomes listed above). The main reason for this is that all four treatments given in the RCTs are evidence-based for at least one of the disorders the patients suffer from (PTSD and PD) and patients who will be assigned to the PTSD-treatment only can given PD-treatment as well after T4 (after 6-12 months) within the research design.

Suicidality or self-injurious behaviour is very common in the study population included for this study. It is also known that starting a new treatment, such as EMDR or DBT could increase symptoms in the beginning, which can develop into suicidal behaviour. SAE's which will occur during the treatment and for which medical care is needed, will be reported to the accredited METC. To monitor the SAE's, patients will be asked to fill in a self-injury questionnaire (*Opzettelijk zelfverwondend gedrag, Baetens & Claes 2014 based on The Brief Non-Suicidal Self-Injury Assessment Tool (BNSSI-AT) van Janis Whitlock en Amanda Purington (2013)*) at the regular assessments. In case of SAE's for which medical care is needed, in between the assessments, therapists will report these incidents to the researchers at the weekly consultations, whom will report these to the accredited METC. The sponsor will report SAEs to the accredited METC that approved the protocol, within 7 days of first knowledge for SAEs that result in death or are life threatening followed by a period of maximum of 8 days to complete the initial preliminary report. All other SAEs will be reported within a period of maximum 15 days after the sponsor has first knowledge of the serious adverse events.

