7.1 Primary study parameters

For population description, the CAPS-5, M.I.N.I.-plus, SCID-5-PD, will be used in addition to the CTQ, LEC-5, DERS, ITQ, PAI-BOR, STAS, PSQI, DES-II, WAV, RSQ, CPI, BDI, AUDIT, WHODAS, EQ5D-5L, and Tic-P will be used (see Table 1). The subgroup of patients that underwent MRI will be compared to the rest of the group to test for pretreatment differences in PTSD severity and type/severity of PD.

The primary analysis in the RCTs will be improvement of PTSD symptoms at 3 time points. This primary analysis will include trauma symptom scores at T₀, T₂ and T₄ (CAPS-5, severity score) in a repeated measurements model, a linear mixed model for repeated measurements including at least time points, treatment group, the interaction between time point and treatment, sex, age and severity as fixed factors, baseline score as covariate and subject as random intercept factor. An cAR(1) structure will be used to model the residual covariance matrix. Responders will be defined as participants with a posttest score at least 1 SD below the pretest score (based on Jacobsen and Truax, 1991).

Secondary analyses will examine whether hormonal and epigenetic factors (5-HTTLPR, BDNF, cortisol/FKBP5-methylation, oxytocin/OXTR) mediate the treatment effects. Mediation analyses will include levels of the aforementioned variables on T₀ and T₂ to estimate the direct and indirect paths of casual treatment on the primary and secondary study parameters, through the proposed mediators.

For individual prediction analyses, machine learning techniques (in R: supervised and unsupervised techniques, e.g. the random forest model method) will be applied to separate treatment responders from non-responders based on clinical and neurobiological candidate predictors and in order to define the predictors

contributing most to classification accuracy, calculating sensitivity, specificity, and positive and negative likelihood ratios from the prediction model (Ball et al., 2014).

Candidate predictors that will be used are:

- Psychological factors: Cognitive factors (educational level/IQ, working memory, emotion regulation), Affective factors (hyperarousal: anger, sleep; hyperarousal: dissociation), and Relational factors (therapeutic alliance, attachment, social support);

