9.6. Public disclosure and publication policy

The results of the study will be submitted for publication in an international peer-reviewed journal adhering to applicable privacy laws and regulations. The principal investigator will determine publication strategy. No treatment group information will be made available until after study completion.

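### The primary CAPS-5 ratings at T2 and T4 are interviewer judgements in an open-label trial, and the plan contains no procedure that masks the raters to arm

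*Combined protocol and SAP*

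**What the plan says.** Section 5.1.1 makes CAPS-5 severity the primary outcome: "All 20 symptoms of PTSD from the DSM-5 are assigned a severity score of 0-4", and the scores are summed. Table 1 lists the CAPS-5 as an interview at T0, T2 and T4. Section 7.1 uses the same three visits: "The primary analysis in the RCTs will be improvement of PTSD symptoms at 3 time points". Section 5.3 confirms the interview at T2 and describes T4 as a repeat of T0 with listed exceptions, none of which is the CAPS-5. The Summary differs, placing T2 among the visits with self-report questionnaires alone; Table 1 and sections 5.3 and 7.1 all put the CAPS-5 there.

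Section 5.2 covers randomisation, blinding and allocation. Its only statement on blinding, in 5.2.2, is "Blinding of participants and therapists to condition is not possible as it will be clear to both therapists and patients which treatment is given". Section 5.2.1 provides independence for one role: "An independent central research assistant will randomize participants to condition".

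The one sentence that names assessors is in the Summary's paragraph on burden and risks. It begins "Assessors will be well-trained and work in close" and ends "connection with the treatment teams". The visit descriptions in 5.3 mention a study intaker at T0 but do not say who rates the CAPS-5 at any visit.

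**The concern.** A CAPS-5 score depends on the interviewer's judgement of each symptom. Patients and therapists know the arm, and Hypotheses A in section 1 predict that integrated treatment will do better. A rater who learns the arm may score, without intending to, in the expected direction. The T2 and T4 scores carry the treatment comparison, so a drift between arms would enter the primary result directly and could not be separated from a treatment effect afterwards. Masking cannot be restored once the ratings have been made.

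The PCL-5, a secondary outcome in 5.1.2, involves no rater judgement. It comes from unblinded patients, however, so it does not replace a masked CAPS-5.

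**Working it through.** **Is there a masking rule anywhere?** The places where one could stand, side by side:

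| Place | What it covers | Does it mask the T2/T4 raters? |
|---|---|---|
| 5.2.1 | Independence of the person who randomises | No; allocation only |
| 5.2.2 | Patients and therapists cannot be blinded | No; raters not mentioned |
| 5.3, T0, T2 and T4 visits | Content of the visits | No; no rater named |
| 5.3, extra contact | A contact for the trauma-treatment-only arm | No; whoever makes it knows the arm, and the person is not identified |
| 6.2.2 | "therapists will report these incidents to the researchers at the weekly consultations" | No; not stated whether raters attend |
| 9.6 | "No treatment group information will be made available until after study completion" | No; publication policy, with no rater or procedure named |
| Summary, burden paragraph | Assessors' contact with the treatment teams | No; and no limit on sharing allocation |

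The document also contains no request that patients conceal their treatment, no log of unmasking and no masked re-rating. Section 5.2, where such text belongs, is present, so removed pages do not explain the gap.

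**How large could it be?** No figure in the plan depends on this point, so there is none to reproduce. What follows is an illustration with assumed drifts, not an estimate for this trial.

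Inputs from section 4.4: SD 20, within-person correlation 0.7, 63 per arm, 25% dropout. Assumed: two-sided 5% test (4.4 states no alpha), no true effect, and a between-arm rating drift d of 1 to 4 points.

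- Patients per arm at T4: 63 × 0.75 = 47.25, taken as 47.
- Drift in SD units: 1/20, 2/20, 3/20, 4/20 = 0.05, 0.10, 0.15, 0.20.
- False-positive rate = P(|Z + d/SE| > 1.96), with Z standard normal.
- T4 adjusted for baseline: residual variance 1 − 0.7² = 0.51; SE = √(2 × 0.51/47) = 0.147 SD.
- T4 unadjusted: SE = √(2/47) = 0.206 SD.

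| Assumed drift (CAPS-5 points) | T4, baseline-adjusted | T4, unadjusted |
|---|---|---|
| 0 | 5.0% | 5.0% |
| 1 | 6.3% | 5.7% |
| 2 | 10.4% | 7.7% |
| 3 | 17.5% | 11.2% |
| 4 | 27.4% | 16.3% |

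Both columns are T4-only contrasts, not the mixed model of section 7.1. As a check on another basis, take 50 per arm and the mean of two follow-up ratings correlated 0.7, without baseline adjustment. Then SE = 20 × √((2/50) × (1.7/2)) = 3.69 points, and drifts of 1, 2 and 4 points give 5.8%, 8.4% and 19.2%. The pattern is the same; the exact level depends on the model and on the drift, which nobody knows.

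**The case against.** The strongest reply is that the plan is silent and does not choose unmasked raters. Section 5.2.2 explains why two groups cannot be blinded and does not put raters among them. Section 9.6 is compatible with masking that was intended but not written down. This stands as far as it goes: what is established is the absence of a procedure, not the presence of bias. It does not meet the point, because an unwritten rule cannot be followed consistently, audited or reported.

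A reader might go further and infer that the raters will know the arm, citing the assessors' contact with treatment teams, the weekly consultations and the extra contact in one arm. The documents do not support that. The first is text about patient burden. The second concerns reports of serious events to researchers who are not identified as raters. The third does not say who makes the contact. These are routes that masking should close, not evidence that allocation reaches a rater.

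It can also be said that masked raters would still be scoring what unblinded patients tell them. That is true, and the benefit is partial. Finally, the number of assessors is not given, so the ease of keeping them separate from treatment staff cannot be verified from the document.

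**Conclusion.** The point holds as a gap in the design as written: the primary outcome is an interviewer rating, patients and therapists are unblinded, the hypothesis is directional, and nothing protects the T2 and T4 ratings from knowledge of the arm. Confidence is high that the procedure is absent. The documents support no statement on whether bias will occur or how large it would be.

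A reader might take the table above as the trial's expected false-positive rate. It is not. The drifts are assumed, the test level is assumed, and the contrasts are simpler than the planned model. The table shows only that drifts well below the 10-point difference used for planning (0.5 × 20 in section 4.4) would matter.

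If the Summary's version of T2 were the operative one, the exposure would lie at T4 alone. The weight of the text is against that reading, and the Summary should be reconciled with Table 1 and sections 5.3 and 7.1. This is an inexpensive improvement, not a fatal defect.

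**What to change.** In 5.2.2 and 5.3, state that the T2 and T4 CAPS-5, and for the same reason the T4 SCID-5-PD, are carried out by the already planned assessors, masked to arm. For each patient, that assessor:

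- is not on the patient's treatment team;
- does not attend therapist consultations about the patient;
- does not make the extra contact reserved for one arm.

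Keep allocation out of the assessor's file, ask patients before each interview not to disclose their treatment, and log every unmasking. Qualify the Summary sentence on assessors and treatment teams so that allocation is not shared with outcome raters. Recording the assessor's guess of the arm, and reporting the PCL-5 difference in SD units beside the CAPS-5, are optional supportive checks.

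The cost is protocol wording, scheduling effort and a breach log. No interview is added. The scheduling effort cannot be quantified because the number of assessors is not stated. Some patients will break the masking, and bias in what unblinded patients report will remain.

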5.3 Study procedures

The study will lead to separate although integrated research projects for 3 PhDs.

A1: Is EMDR treatment more effective compared to integrated DBT-EMDR in patients with PTSD with comorbid BPD?

1. Systematic review and meta-analysis: do personality or dissociative symptoms predict effectiveness of PTSD treatment?
2. Do patients in the present study show higher response rate and effect sizes in integrated DBT-EMDR-treatment compared to EMDR-treatment alone after 12 months?
3. Is DBT-EMDR-treatment more effective as compared to EMDR-treatment alone in terms of PD symptoms, general psychiatric symptoms, disability, quality of life and health costs?
4. Do psychological (cognitive, affective, relational) factors predict (integrated DBT-) EMDRtreatment outcome?

A2: Is ImRs more effective compared to integrated SFT- ImRs in patients with PTSD with comorbid CPD?

1. Systematic review and meta-analysis: do personality or dissociative symptoms predict effectiveness of PTSD treatment?
2. Do patients in the present study show higher response rate and effect sizes in integrated SFT- ImRs -treatment compared to ImRs -treatment alone after 6-12-18 months?
3. Is SFT- ImRs -treatment more effective as compared to ImRs -treatment alone in terms of PD symptoms, general psychiatric symptoms, disability, quality of life and health costs?

4. Do psychological (cognitive, affective, relational) factors predict (integrated SFT-) ImRs treatment outcome?

B: Predictors of PTSD-treatment

1. Literature review: what is known on working mechanisms of PTSD treatment and do neurobiological findings predict PTSD treatment outcome?
2. Are PTSD treatments in this PTSD + PD population mainly working on increasing extinction of fear responses? Is this associated with decreasing salience, negative affect and cognitive control network activity and connectivity?
3. Do biomarkers (ACC volume, amygdala and ventral ACC and dorsal ACC activity, and/or hormonal/epigenetic factors (5-HTTLPR, BDNF, cortisol/FKBP5-methylation, oxytocin/OXTR) individually predict treatment outcome of PTSD treatment?

Timing of assessments

Baseline (To) visit

All patients coming to the Sinai Center are asked to fill in the ROM questionnaires before the intake as part of standard care (OQ-45, LEC-5/PCL-5, SCID-5-PD screener, see Table 1). As part of the standard intake procedure at the Sinai Centre, patients who score positively on the SCID-5PD screener will be interviewed with the M.I.N.I.-plus and the SCID-5-PD. Patients with potential eligibility based on the in- and exclusion criteria described earlier receive the study information folder from the psychologist who performed the intake with them. If a patient is interested and gives their consent, the intaker informs the researchers to contact the patient. One of the researchers will explain the study to the possible participant and provide the information folders. After a consideration period of at least one week, they will be asked whether they want to take part in the research.

At To/Day 1, the study- intaker will explain the study information once more. If informed consent is obtained, in- and exclusion criteria will again be checked to assess the patient's potential eligibility for participation (Dutch language, , LEC-5/PCL-5, SCID-5-PD screener) and if the patient is included, the CAPS-5 will be performed.

After the interview, the patients receive an online code to fill in additional questionnaires online at the center or at home, if the patient has access to the internet (see Table 1). Total duration of the measurements of To/Day 1 will be ca. two hours (see Table 3).

At To/Day 2, patients are invited for the physical examination (weight and height to calculate Body Mass Index (BMI), blood pressure, hair sample by a research assistant and fasting blood sample as well as questions on cigarette smoking, alcohol and coffee consumption, medication and drug use) and they will be asked to perform a working memory task (N-back-task) outside the scanner and to fill in the last set of questionnaires (see Table 1) either at the Sinai Center or online at home. Total duration of the measurements of To/Day 2 will be ca. 40 minutes (see Table 3).

Blood samples will be collected in 3 x 6ml tubes and the frozen samples will be stored at -80°C for intended future assaying of inflammatory markers (see Coelho et al., 2014), neuropeptides (such as oxytocin, 5HT), and epigenetics (such as FKBP5-methylation, OXTR- & 5HTTLPRgenes). The tubes will be stored without personal data linked to it, and they will only be marked with a subject number as described in section 9.1. below. Cortisol level (HPA-indicator) will be assessed in hair. This sample can be collected non-invasively by cutting a 1-cm distal to the scalp (1 month's exposure) sample of hair (Russell et al., 2012). All samples will be stored for 15 years (according to Archiefwet 1995).

In a subgroup: MRI session

Exclusion criteria for MRI research will be checked (metal implants, pregnancy, somatic disorders interfering with brain functioning, other (psycho-)pharmaca than at-least-3-months stabile dose SSRI or low-dose benzodiazepines, claustrophobia). A separate visit for MR scanning will be planned within 2 weeks of To, before the start of treatment, without causing a delay in treatment start. MRI sessions take at maximum 60 minutes (30-min functional MRI with a face recognition, and a suppression vs. reappraisal task, 5-min structural MRI, 8-min resting state MRI; and 8-min DTI) plus 30 min preparation. Next to patients, 40 healthy control persons, matched for age, gender, and education, will be asked to participate in one MRI session (no repeat MRI). These healthy control persons will be recruited via advertisements in local papers.

T1, T3 and FU

Patients do not have to come to the study center for T1, T3 and FU and can fill in the questionnaires via a login code at home if they have access to the internet (see Table 1.). Child trauma and life events questionnaires are only done at baseline (CTQ, LEC-5). Total duration of these measurements (T1, T3 and FU) will be between 15 and 30 minutes (see Table 3).

T2 visit

From all participants whose blood and hair was collected at baseline, blood and hair will be collected at T2 as well (duration 30 minutes). All participants who participated in the fMRI study at baseline will have their second MRI at T2. (duration 90 minutes). At T2, the CAPS-5 will also be conducted and participants will fill out the same questionnaires as at T0, except for the CTQ and LEC-5. Total duration of these measurements of will be ca. 2 hours (see Table 3).

Extra contact moment

For participants in the trauma-treatment only group, there will be an extra moment of contact 3 months after T3, with a short reminder about the following measurements and attention for the wellbeing of the client.

T4 visit

This is the same as T0, except for the informed consent procedure and except for the N-back task and physical examination and trauma questionnaires that will be done at T0 only (CTQ, LEC-5). Total duration of these measurements will be 4,5 hours (see Table 3).

Treatment visits

These will be scheduled as usual. For durations of specific treatments see 3.

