Use of co-intervention: Patients may continue taking medication for PTSD throughout the study. Patients who started with new medication for PTSD within 1 month prior to the initial screening will be excluded from participation. No other psychological or new pharmacological therapy is allowed during treatment. Medication use is monitored during the study.

Escape medication/treatment: Participants might start taking medication or another form of treatment/therapy in case of acute crisis during the study. The use of these medications or crisis intervention during the study as co-intervention will not lead to exclusion from the study, but will be monitored, documented, and reported.

Further treatment: After completion of the EMDR or ImRs a first follow-up assessment will be completed and the therapist will see the patient for an evaluation. If more treatment is acutely needed, a clinical evaluation is done and the indication staff will decide what treatment to offer to the patient. The kind, intensity and frequency of this further treatment will be monitored, documented and reported. All patients in Zorgpad 1 are allowed to start SFT or DBT after T4 (i.e. 6 months after completing Zorgpad 1).

18

Figure 2. Flow chart for two connected randomized controlled trials (RCTs) for patients with PTSD and borderline personality disorders (BPD) resp. with PTSD and cluster C personality disorders (CPD)

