TIME POINTS (months)				0	3	6&	9	12	18
SCREENING	ROM Questionnaires	Items							
Psychiatric symptoms	OQ-45.2 (1996)	45	SR	X*	X	X	X	X	X
PTSD symptoms	PCL-5 1.1 (2014)	22	SR	X*	X	X	X	X	X
PD symptoms	SCID-5-PD screener	119	SR	X					
Axis I disorders	SCID-5-S screener	??		X*					
INTERVIEWS	DAY 1	Semi-structured interviews	Duration	Type					
PTSD	CAPS-5 1.2 (2015)	45 min	INT	X		X		X	
Axis I-disorders	SCID-5-S	45 min	INT	X*#				X	
Personality disorders	SCID-5-PD	120 min	INT	X#				X	
QUESTIONAIRES	DAY1	Additional questionnaires	Items						
Demographics	Demographic questionnaire PROSPER (2017)	30	INT	X*					
Life events	LEC-5 1.1 (2014)	17	SR	X*					
Child trauma	CTQ (NESDA 2004)	25	SR	X					
Emotion regulation	DERS NL (2004)	36	SR	X		X		X	
Complex PTSD	ITQ (2018)	9	SR	X		X		X	
Anger	STAS NL (ZAV 1982)	10	SR	X		X		X	
Sleep	PSQI NL (1989)	10	SR	X		X		X	
Dissociation	DES-II (1986)	28	SR	X		X		X	
Depression severity	BDI-II (2002)	21	SR	X		X		X	
Alcohol / drugs	AUDIT (MATE-nl 2.1 2010)	10	SR	X		X		X	
Self harm behaviour	NSSI screening (NL versie 2014)	7	SR	X	X	X	✘	X	X
Borderline personality symptoms	PAI-BOR (2009)	24	SR	X		X			✘

DAY2	Additional Questionnaires								
Therapeutic alliance	WAV (1990)	12	SR		✗	X	X		
Attachment	RSQ (1994)	30	SR	X		X		X	
Social support	CPI (NESDA 2004)	4	SR	X		X		X	
General functioning	WHODAS 2.0 (2014)	12	SR	X		X		X	X
Quality of life	EQ-5D-5L 2 (2010)	9	SR	X		X		X	X
Health care consumption	Tic-P (2012)	32	SR	X		X		X	X

AUDIT = Alcohol Use Disorders Identification Test; BDI = Beck Depression Inventory;; CPI = Close Person Inventory; CTQ = Child Trauma Questionnaire; DES-II = Dissociative Experiences Scale; INT = interview; LEC-5 = Life Events Checklist; SCID-5-S; OQ-45 = Outcome Questionnaire 45; PCL-5 = PTSD Checklist for DSM-5; PSQI = Pittsburg Sleep Quality Index; ROM = Routine Outcome Measurement; RSQ = Relationship Scale Questionnaire; DERS = Difficulties in Emotion Regulation Scale; ITQ = International Trauma Questionnaire; SR = self-report questionnaire; SCID-5-PD = Structured Clinical Interview for DSM-5 Personality disorders; STAS = State Trait Anger Scale; Tic-P = Trimbos/iMTA questionnaire for costs associated with psychiatric illness; WAI = Working Alliance Inventory, WHODAS = World Health Organization Disability Assessment Schedule 2.0.; NSSI = Non Suicidal Self-Injury screener; PAI-BOR: Personality Assessment Inventory- Borderline features scale.

* Healthy controls will only fill out these questionnaires and interviews

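### A2's 18-month comparison with ImRs alone has no CAPS-5 behind it, and by then the ImRs-only arm may have started SFT or DBT

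*Combined protocol and SAP*

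**What the plan says.** Section 5.3, A2 question 2, asks about response rate and effect sizes for integrated SFT-ImRs "compared to ImRs -treatment alone after 6-12-18 months". The matching A1 question asks for the comparison "compared to EMDR-treatment alone after 12 months" and goes no further.

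The Summary sets one endpoint time for the whole study: "Primary outcome measure is PTSD symptom severity after 12 months". Section 5.1.1 names the CAPS-5 as the primary instrument. Section 7.1 gives one model for both RCTs: "This primary analysis will include trauma symptom scores at T₀, T₂ and T₄ (CAPS-5, severity score". It then adds: "Responders will be defined as participants with a posttest score at least 1 SD below the pretest score". That sentence names no instrument and no time point.

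Table 1 marks the CAPS-5 at T0, T2 and T4 only, and the PCL-5 at all six time points. The Summary says that at 3, 6, 9 "and 18 months (follow-up), questionnaires only will be used". Table 1 and section 5.3 do add a CAPS-5 at 6 months, but nothing adds one at 18.

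Under Further treatment, section 3 states: "All patients in Zorgpad 1 are allowed to start SFT or DBT after T4". Section 6.2.2 confirms that this later PD treatment belongs to the research design.

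**The concern.** Two parts of the 18-month question do not fit the design: the measure and the comparator. Response and effect size on the primary instrument cannot be obtained at a visit where that instrument is not administered. An arm whose patients may have begun PD treatment six months earlier is no longer ImRs alone.

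An analyst who followed section 5.3 literally would use the PCL-5 at 18 months and report the result as integrated treatment against ImRs alone. If the difference had shrunk, it could be read as fading benefit of integrated treatment, when part of the cause might be catch-up in the comparator arm. Section 7 does not say which 18-month measure is meant, which SD the responder rule would use on it, or how PD treatment after T4 is handled. Those choices would be open after the data are seen.

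**Working it through.** **Step 1. Question against schedule** (Table 1; section 5.3)

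| | T0 (0) | T1 (3) | T2 (about 6) | T3 (9) | T4 (12) | FU (18) |
|---|---|---|---|---|---|---|
| CAPS-5 interview | X | | X | | X | |
| PCL-5 self-report | X | X | X | X | X | X |
| Asked for in A2 question 2 | | | yes | | yes | yes |

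The blank at 18 months is not a table-reading accident. Table 3 allots no interview time to follow-up, section 5.3 lets patients complete follow-up online at home, and the section 7.1 model ends at T4. The 6- and 12-month parts of the question are covered by the CAPS-5; the 18-month part is not.

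**Step 2. What the arms have received by 18 months**

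Integrated treatment lasts 12 months (section 3). In the ImRs-only arm, SFT or DBT is permitted after T4 but not required. Follow-up comes 18 − 12 = 6 months later, so a patient who starts at once could have had about half of a one-year PD treatment. The contrast by randomised arm is then integrated treatment at once versus ImRs with optional later PD treatment.

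**Step 3. The plan's reference difference**

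Section 4.4 uses a 0.5 SD difference with SD 20 (10 CAPS-5 points), within-person correlation 0.7 and 5 follow-up measurements. With two-sided alpha 0.05 (assumed, as none is stated):

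n = 2 × (1.96 + 0.842)² × 20² × [1 + 4 × 0.7] / (10² × 5) = 47.7, so 48 per arm.

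The plan states 50, which this reproduces closely. The sample size is not at issue here; the check only confirms 0.5 SD as the working difference.

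**Step 4. Illustrative dilution**

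Let u be the share of the ImRs-only arm that starts PD treatment and g the mean gain by 18 months in those who start. Neither is in the documents. If the 0.50 SD difference is otherwise maintained:

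D = 0.50 − u × g

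- u = 0: D = 0.50 SD
- u = 0.5, g = 0.25: D = 0.50 − 0.125 = 0.375 SD (7.5 points at SD 20)
- u = 1, g = 0.25: D = 0.25 SD (5 points)
- u = 1, g = 0.50: D = 0

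For power at a single time point, take 63 × 0.75 = 47 completers per arm and SD 20. The unadjusted standard error is 20 × √(2/47) = 4.13. With baseline adjustment at correlation 0.7 it is 4.13 × √(1 − 0.49) = 2.95. Power is Φ(D/SE − 1.96).

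| D | Unadjusted | Baseline-adjusted |
|---|---|---|
| 0.50 SD | 68% | 92% |
| 0.375 SD | 44% | 72% |
| 0.25 SD | 23% | 40% |

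These rows carry CAPS-5 planning values over to a PCL-5 comparison in SD units, which is a further assumption. They show the direction and the possible range of the effect, not its expected size.

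**The case against.** The strongest reply is that the 18-month data are usable. The PCL-5 is a listed secondary outcome (section 5.1.2), is collected at 18 months, and has priority when patients drop out of treatment (section 5.6). A response rate under a 1 SD rule and an effect size can both be computed from it. Later PD treatment is optional and sequential, so the comparison by randomised arm remains a valid comparison of strategies. A reader might infer that the 18-month question cannot be answered at all; the documents do not support that.

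A reader might also infer that the two RCTs have different primary time points. They do not. The Summary and section 7.1 set one 12-month outcome and one CAPS-5 model for both, and the hypotheses and objectives for A1 and A2 are parallel and name no 18-month time. Section 5.3 lists research questions for the PhD projects; it does not define endpoints.

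Nor do the documents say that the CAPS-5 defines response. That is a fair reading from where the sentence stands in section 7.1, but the instrument is not named.

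Finally, section 3 already promises to document and report further treatment, though it says so of treatment that is acutely needed, and the Tic-P records health care use at 18 months.

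All of this stands, and it narrows the point. It does not rescue the wording. The question names ImRs alone as comparator at a time when the design no longer guarantees that condition, and the plan nowhere says that 18-month response would come from the PCL-5, a self-report by patients who know their treatment (section 5.2.2).

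**Conclusion.** The point holds for the 18-month part of A2 question 2 only. At 18 months there are no CAPS-5 data, and a comparison by randomised arm estimates integrated treatment at once versus ImRs with optional later PD treatment. It cannot support a conclusion about ImRs alone.

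The size of any dilution is unknown, because the documents give neither uptake nor benefit of the later treatment. Under the assumptions shown, a 0.50 SD difference could stay at 0.50 SD, fall to 0.375 or 0.25 SD, or in the extreme vanish. The absence of the CAPS-5 and the change of comparator do not depend on those assumptions.

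The 12-month primary endpoint and the 6-month CAPS-5 comparison are unaffected. This calls for a correction to one research question; it is not a flaw in the primary analysis.

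**What to change.** In section 5.3, limit A2 question 2 (CAPS-5 response and effect size against ImRs alone) to 12 months, the primary time already set in the Summary and used in A1, with 6 months secondary.

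Add 18 months as a separate secondary comparison on the PCL-5, by randomised arm, labelled as a comparison of assigned strategies. Report beside it how many ImRs-only patients started PD treatment and when. If a PCL-5 response rate is reported, state in advance which SD the 1 SD rule uses. Draw no conclusion about ImRs alone at 18 months. Inference on the strategy comparison need not be barred; that would be a matter of preference.

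The change is one of wording and reporting. It needs no extra assessment and leaves the treatment rules as they are. The cost is giving up an 18-month claim against ImRs alone, which the design cannot support.
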